9.3.3 Sensitivity and Supplementary Analyses of the Primary Efficacy Endpoint(s)

9.3.3.1 Sensitivity Analyses

The sensitivity analyses of the primary endpoint will include imputation using the copyreference approach, and an alternate handling of intercurrent events.

The copy-reference approach is one type of pattern-mixture models (PMM), under which data could be missing-not-at-random (MNAR), with repeated analyses combined via the reference based multiple imputation (MI) procedure. This approach is to assess the robustness of the MMRM analysis to possible violation of the missing-at-random (MAR) assumption in the primary analysis.

Step 1. Missing values will first be imputed by the Markov Chain Monte Carlo (MCMC) in order to attain monotone missingness. The MCMC imputation assumes MAR for intermittent missing data. The MCMC method will be implemented using SAS PROC MI, with the use of option IMPUTE = MONOTONE in the MCMC statement. The rest of the missing data will then follow a monotone missing pattern.

Step 2. Implementation of the copy-reference method are as follows:

- 1. The reference-based approach uses the placebo group as the reference. The missing values in the reference group are imputed using the observed data overall in that group under the MAR assumption. The missing pattern is defined by the participant's last visit with a non-missing value. The mean vector and the covariance matrix of the multivariate normal distribution are estimated for the reference group.
- 2. For ABBV-552 treatment groups, missing values are imputed based on the distribution estimated from the reference group (placebo group).

The first PROC MI will be performed 100 times using MCMC method for partial imputation of the data with a non-monotone missing pattern. The output dataset will then be used as the input dataset for the next PROC MI. Note that the output dataset already contains 100 copies of the original dataset. With the next invocation of MI procedure, the missing data will be filled in (Steps 1 and 2) for the existing copies. This is achieved with the use of NIMPUTE=1 and a BY _Imputation_ statement. Finally, each of the 100 imputed datasets will be analyzed using an analysis of covariance (ANCOVA) model. The model includes treatment group and randomization stratum as main effects, and baseline ADAS-Cog 14 score as a covariate. The LS mean difference and corresponding SE are estimated from the model comparing each ABBV-552 treatment group with the placebo group. The ANCOVA analysis results from 100 completed datasets are combined for overall estimation and inference using Rubin's rule² to produce a pooled estimate of LS mean difference and its SE. This copy-reference approach sensitivity analysis will be performed on mITT analysis set and safety analysis set.

Two additional sensitivity analyses of the primary endpoint will be provided by alternatively handling the intercurrent events:

ABBV-552
M23-515 – Statistical Analysis Plan
Version 3 – 20 September 2024

- 1. Efficacy data collected after a start, stop or dose change of AD medication during the study will be included in the primary analysis. The same MMRM as specified in the primary analysis will be used.
- Efficacy data collected after participant discontinued study treatment will be excluded in the primary analysis. The same MMRM as specified in the primary analysis will be used.

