4.0 Analysis Sets

The following analysis sets will be used.

The Intent-to-Treat analysis set includes all randomized participants and participants will be grouped according to treatment as randomized.

The modified Intent-to-Treat (mITT) analysis set includes all randomized participants who received at least 1 capsule of study drug and have at least 1 post-baseline ADAS-Cog 14 score. The participants will be grouped according to treatment as randomized. The mITT analysis set will be used for all efficacy analyses, including baseline efficacy summaries.

The safety analysis set consists of all participants who received at least 1 capsule of study drug. The participants will be grouped according to treatment actually received the majority of the time. This will be defined based on the number of days each treatment is received. The safety analysis set will be used for all safety analyses and demographic analyses, unless otherwise noted.

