5.0 Participant Disposition

A summary of participant accountability by country and investigator will be provided where the number of participants in each of the following categories will be tabulated for each treatment group for the Intent-to-Treat Analysis Set:

ABBV-552
M23-515 – Statistical Analysis Plan
Version 3 – 20 September 2024

- Participants randomized in the study;
- Participants who took at least one dose of study treatment;
- Participants who completed study treatment;
- Participants who prematurely discontinued study treatment;
- Participants in each analysis population, as applicable.

The summary of participant accountability by investigator also will include the number of participants who screened and the number of participants who screen failed and will be summarized for all participants.

[figure not shown]
The number and percentage of participants in the safety analysis set who prematurely discontinued study treatment will be summarized by reason for not completing study treatment overall and by treatment group.

The number and percentage of participants in the safety analysis set who did not complete the protocol defined follow-up period will be summarized by reason for not completing study overall and by treatment group.

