14.0 Version History

Table 3. SAP Version History Summary

[figure not shown]
Version	Date	Summary	
1.0	12 July 2023	Initial version	
2.0	2 May 2024	Update to clarify the definition of analysis sets.	
		Update to clarify the definition of number of capsules that should have been taken.	
		Update to exclude efficacy data collected after blind broken.	
		Update to replace posterior probability with p-value statistic to efficacy analysis.	
		Added sensitivity analysis to primary endpoint using safety analysis set.	
		Removed weight-by-sex summary analysis.	
		Update to modify C-SSRS analysis.	
		Removed lab/vital sign comparison between treatment groups	
3.0	20 September 2024	Updated analysis for vital signs.	
		Added language for conducting additional subgroup analysis given sufficient data.	

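### The safety-set run of the copy-reference analysis groups by treatment received, so the effect of the added participants cannot be told from the effect of regrouping

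*SAP*

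**What the plan says.** SAP 4.0 defines three sets.

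- **Intent-to-Treat (ITT):** "The Intent-to-Treat analysis set includes all randomized participants and participants will be grouped according to treatment as randomized".
- **mITT:** randomised participants who "received at least 1 capsule of study drug and have at least 1 post-baseline ADAS-Cog 14 score", also grouped as randomised.
- **Safety:** "The safety analysis set consists of all participants who received at least 1 capsule of study drug". For grouping: "The participants will be grouped according to treatment actually received the majority of the time", counted by days on each treatment.

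SAP 9.3.3.1 says of the copy-reference analysis of ADAS-Cog 14: "This copy-reference approach sensitivity analysis will be performed on mITT analysis set and safety analysis set". Its stated aim is: "This approach is to assess the robustness of the MMRM analysis to possible violation of the missing-at-random (MAR) assumption in the primary analysis". Placebo is the reference group, and its estimated distribution supplies the missing values in all three active arms.

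The version history (SAP 14.0) lists under version 2.0: "Added sensitivity analysis to primary endpoint using safety analysis set". It gives no reason. The only named use of the ITT set is participant accountability (SAP 5.0), where counts are "tabulated for each treatment group for the Intent-to-Treat Analysis Set".

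**The concern.** An efficacy robustness check should keep the randomised groups. SAP 9.3.3.1 does not set aside the received-treatment grouping, so a programmer who follows the text would produce an as-treated comparison for the second run.

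That run is worth getting right. The primary MMRM and the two alternative intercurrent-event analyses are on mITT, so all of them leave out participants with no post-baseline ADAS-Cog 14 score. Table 1 of the SAP names the estimand population as participants with mild Alzheimer's disease, which is wider than mITT. The safety-set run is the only one that brings any of the excluded participants back.

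It changes two things at once relative to the mITT run: who is included and how they are grouped. If the two runs disagree, the reader cannot say which change was responsible. Regrouping also reaches further than one arm. A participant with observed scores who moves into or out of placebo alters the reference distribution, and so the imputed values in every active arm.

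**Working it through.** **1. The plan's own figure.** Inputs from SAP 2.4 are a difference of 2.85, SD 5.7, 60 per group, 20% discontinuation and two-sided alpha 0.10. Evaluable per arm: 60 × 0.80 = 48. SE = 5.7 × √(2/48) = 1.16. The normal approximation gives power Φ(2.85/1.1635 − 1.645) = Φ(0.805) = 78.9%, which agrees with the stated value of about 80%. Nothing below changes that figure.

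**2. What differs between the runs.**

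| Analysis | Set | Grouping | Baseline-only participants |
|---|---|---|---|
| Primary MMRM | mITT | As randomised | Excluded |
| Copy-reference, run 1 | mITT | As randomised | Excluded |
| Copy-reference, run 2 | Safety | As received | Included if dosed |

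The primary analysis against run 1 shows the effect of the imputation approach alone. Run 1 against run 2 shows added participants and regrouping together.

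**3. Size of regrouping.** The documents give no count of participants on the wrong treatment, so k = 1 to 3 of 60 is an assumption. This is simple arithmetic on group means, not a simulation of the imputation.

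- *Prognosis equal to the arm average.* As randomised, the difference is 2.85 × (1 − k/60); as received, it stays at 2.85. The gap is 2.85 × k/60 = 0.05 (k = 1) to 0.14 (k = 3), or about 4% to 12% of the SE of 1.16.
- *Prognosis 1 SD (5.7 points) from average, assumed, with a move from active to placebo.* The shift in the as-treated difference is 5.7 × k × [1/(60 − k) + 1/(60 + k)].
  - k = 1: 5.7 × (1/59 + 1/61) = 0.19
  - k = 2: 11.4 × (1/58 + 1/62) = 0.38
  - k = 3: 17.1 × (1/57 + 1/63) = 0.57

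The direction depends on the sign of the prognosis. With k = 0 the grouping makes no difference.

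**4. Size of adding undosed participants.** If u of 60 in an active arm took no capsule and were imputed as placebo, an effect of 2.85 becomes 2.85 × (1 − u/60): 2.85, 2.80, 2.76 and 2.71 for u = 0, 1, 2 and 3. The values of u are also assumed.

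**5. How many participants the second run could add.** If the 20% loss falls at a constant rate over 12 weeks, 60 × (1 − 0.8^0.5) = 6.3 per arm leave before Week 6. Under that loss pattern this is an upper-end count. Protocol Appendix D also schedules ADAS-Cog 14 at the premature discontinuation visit, and a score there puts the participant in mITT.

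**The case against.** The case against giving this weight is strong, and much of it stands.

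- **Imputation is not confounded with regrouping.** A reader might infer that, if the safety-set result departs from the primary result, imputation and regrouping cannot be told apart. The documents do not support this, because the mITT run is grouped as randomised and isolates imputation.
- **Intent is not stated.** A reader might also infer that the safety-set run was added to recover participants outside mITT. That is plausible, since dosed participants with no post-baseline score are the only people it adds to mITT. But SAP 9.3.3.1 gives robustness to MAR as the aim, and the version history gives no reason.
- **The count of about 6 per arm does not argue for changing the set.** Those participants took study drug and are already in the safety set. The figure shows why the check has some use, and it is an upper-end one.
- **The triggering events should be rare.** Protocol 4.1 places randomisation and first dose at the same clinic visit, and Protocol 5.7 has the IRT assign kits. By nominal days, one wrong dispensing at Week 6 covers Days 43 to 84, which is 42 of 84 days and not a majority.
- **Other outputs help.** SAP 5.0 tabulates participants in each analysis population by treatment group, and SAP 7.3 counts wrong-treatment deviations.

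Three limits apply. The half-of-days margin is thin: a last dose on Day 85 makes it 43 of 85. For an early leaver, the kind of participant this run adds, a single dispensing can decide the group. The SAP 7.3 category combines wrong treatment with incorrect dose, so it does not identify who was regrouped.

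**Conclusion.** The point holds in a limited form. As written, one of the two copy-reference runs is an as-treated efficacy comparison, although the SAP defines an as-randomised ITT set that it uses only for accountability. The consequence is that the effect of adding participants cannot be separated from the effect of regrouping them. The primary analysis, the mITT copy-reference run and the two MMRM variants all keep the randomised groups and are not touched.

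The expected size is small. With 1 to 3 participants per arm mainly on the wrong treatment, the gap is 0.05 to 0.14 points if their prognosis is average, and the shift is 0.19 to 0.57 points if it lies 1 SD away. Both the counts and the 1 SD are assumptions. If nobody is undosed or mainly received the wrong treatment, the choice makes no difference. Since this is also a sensitivity analysis in a hypothesis-generating Phase 2b study without Type I error control, the severity is minor. The reason to act is that the correction is cheap.

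**What to change.** In SAP 9.3.3.1, name the Intent-to-Treat analysis set, grouped as randomised, in place of the safety analysis set for the second copy-reference run. Two details need a sentence each:

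1. Limit the run to participants with a baseline ADAS-Cog 14 score. This narrows the SAP's ITT definition and should be stated as such. Say also that participants with a baseline score only are imputed from the placebo distribution given baseline.
2. Give a baseline rule for anyone undosed, because SAP 7.1 defines baseline relative to first administration. The last value on or before randomisation would serve.

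The minimum alternative is to keep the safety set and state that, for this analysis, participants are grouped as randomised. This needs no new baseline rule but still omits anyone randomised and never dosed.

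Either way the cost is one wording change with the same programs; the ITT option also needs the baseline rule.

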9.3.3.2 Supplementary Analyses

The group mean difference between each treatment group and placebo at Week 6 will be based on the same MMRM model noted in Section 9.3.1.

The change from baseline in ADAS-Cog 14 effect size will be calculated for each treatment group at Weeks 6 and 12.

9.4 Additional Efficacy Endpoints and Analyses

9.4.1 CDR

The change from baseline in the CDR-SB will be analyzed at Week 12 using an ANCOVA including treatment group and the randomization stratum as main effects and the baseline CDR-SB as a covariate.

The effect size for each treatment group over placebo will be provided.

A shift table from baseline to Week 12 of the number and percentage of participants in each category of the CDR global score, as well as missing, will be provided by treatment group.

9.4.2 MMSE

The change from baseline in the MMSE total score will be analyzed at Week 12 using an ANCOVA including treatment group and the randomization stratum as main effects and the baseline MMSE total score as a covariate.

[figure not shown]
The effect size for each treatment group over placebo will be provided.

9.4.3 Cogstate Brief Battery (CBB) and International Shopping List Test (ISLT)

The CBB consists of the following components: detection test [DET], identification test [IDN], one card learning [OCL], and one back test [ONB]. The ISLT consists of the following: ISLT-Immediate Recall and ISLT-Delayed Recall. Together, the CBB and ISLT are referred to as the Cogstate Computerized Battery (CCB).

The change from baseline for the CCB will be analyzed using an MMRM including treatment group, visit, treatment-by-visit interaction, and the randomization stratum as fixed effects and the baseline score as a covariate. The unstructured covariance structure will be used to estimate the within-participant variance-covariance. Denominator degrees of freedom will be computed using the Kenward-Roger method. The group mean treatment difference between each dose and placebo at Weeks 1, 2, 6, and 12 will be based on contrasts from this model. If the model fails to converge with an unstructured covariance structure, the compound symmetry (CS) covariance structure will be substituted. If the model still fails to converge, data will be analyzed as observed using an ANCOVA model with treatment and the randomization stratum as main effects and the baseline of the measure being analyzed as a covariate.

This will be calculated for the primary outcome measures (e.g., reaction time, accuracy, correct responses) for each component of the CCB as well as the global and domain-specific (attention domain, learning/working memory, and episodic memory) composite scores. The primary outcome measures and calculation details of the composite scores may be found in Appendix C.

Additionally, the effect sizes for the change from baseline for each component of the CCB will be calculated at Weeks 1, 2, 6 and 12.

9.4.4 Neuropsychiatric Inventory (NPI)

The change from baseline in the NPI will be analyzed at Week 12 using an ANCOVA including treatment group and the randomization stratum as main effects and the baseline MMSE as a covariate.

This will be done for the total (frequency x severity) and caregiver distress scores for each behavioral domain, as well as the total NPI score and the total distress score.

The effect size for each treatment group over placebo will be provided.

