4 INVESTIGATIONAL PLAN

4.1 Overall Study Design and Plan

This is a Phase 2b, proof-of-concept, dose-finding, multicenter, double-blind, randomized, placebo-controlled study to evaluate the safety, efficacy, PK, and PD of ABBV-552 in participants with mild AD.

This study will enroll approximately 240 participants with mild AD between 50 and 90 years of age. Participants may be naïve to AD therapy or be on a stable dose of AD therapy which should remain unchanged throughout the study. Participants who discontinued prior AD therapies at least 90 days before Screening Visit 1 may also participate; reason(s) for discontinuing prior AD therapies must be recorded.

The study will consist of a Screening Period of approximately 30 days, a Double-Blind Treatment Period of 12 weeks, and a Safety Follow-up Period of 30 days.

Two clinic visits will be completed during the Screening Period: Screening Visit 1 and Screening Visit 2. Procedures required to evaluate participant eligibility at Screening Visit 1 will include neuropsychological/clinical assessments, a clinical laboratory panel, ECG, MRI, and neurological and physical examinations. MRI may be performed anytime during the screening period, but with sufficient time to allow for central read and confirmation of eligibility prior to Baseline Day 1.

If a participant fails initial screening, the site must contact the sponsor if a participant would like to consider rescreening. All assessments must be repeated during rescreening with the following exceptions: MRI assessment does not need to be repeated if it was performed within 6 months of the rescreening visit and if there has been no significant change in the participant's medical condition per investigator's discretion.

Following the confirmation of eligibility at Screening Visit 1, with the exception to MRI, participants will return for Screening Visit 2 where the cognitive assessments (which include ADAS-Cog 14, Cogstate Computerized Battery, and Altoida DNS) will be repeated for familiarization purposes. Screening Visit 2 must take place at least 7 days after Screening Visit 1 and at least 7 days before Baseline/Day 1.

Where relevant, participants undergoing methylmalonic acid (MMA) reflex testing but who are otherwise eligible may proceed to Screening Visit 2 while MMA testing takes place in parallel; however, Baseline/Day 1 must occur only after their MMA results confirm that there is no vitamin B₁₂ deficiency.

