5 STUDY ACTIVITIES

5.1 Eligibility Criteria

Participants must meet all of the following criteria in order to be included in the study. Anything other than a positive response to the questions below will result in exclusion from study participation.

Consent

- 1. Participant or their legally authorized representative must voluntarily sign and date an informed consent, approved by an independent ethics committee (IEC)/institutional review board (IRB), before the initiation of any screening or study-specific procedures.
- 2. Participant has a study partner who:
 - Spends a minimum average of 10 hours per week with the participant.
 - Is able and willing to accompany the participant to study visits and be available by telephone at designated visits throughout the duration of the study.
 - According to the investigator's opinion, is able and willing to complete the protocol-specified questionnaires.
 - Must provide a separate Independent Ethics Committee/Institutional Review Board (IEC/IRB) approved written informed consent to participate in the study.

Demographic and Laboratory Assessments

- 3. Adult male or female, between 50 and 90 years of age, inclusive, at the time of consent.
- 4. Participant must not have any contraindications or inability to tolerate MRI.
- 5. Participant must have a body mass index of 18 to 33 kg/m², inclusive.
- 6. Participants are willing and able to comply with procedures required in this protocol.
- 7. Participants must have adequate renal function as defined by eGFR ≥ 60 mL/min.
- 8. Participants must have adequate hepatic function as defined by:
 - Alanine aminotransferase increased ≤1.5 x ULN of normal

- Aspartate aminotransferase increased ≤ 1.5 x ULN of normal
- Total bilirubin ≤ 1.8 mg/dL, with the exception of participants with Gilbert's syndrome

Disease/Condition Activity

Participant meets the following disease activity criteria:

- 9. Diagnosis of probable Alzheimer's disease according to the National Institute of Aging-Alzheimer's Association (NIA-AA) (2011) criteria.
- 10. MMSE score of 20 to 26 at Screening Visit 1.
- 11. Clinical Dementia Rating Scale (CDR) global score of 0.5 or 1, CDR memory score of 0.5 or higher, and at least 1 CDR functional domain (community affairs, home and hobbies, or personal care) score of 0.5 or higher at Screening Visit 1.

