7.4 Statistical Analyses for Efficacy

Analysis of the primary and all other efficacy endpoints will be conducted on the mITT analysis set based on 2-sided α = 0.1 level, unless otherwise specified in the SAP.

Summary and Analysis of the Primary Endpoint

The primary analysis of ADAS-Cog 14 will be conducted using an MMRM including treatment group, visit, treatment-by-visit interaction, and the randomization stratum as fixed effects and the baseline ADAS-

Cog 14 score as a covariate. The unstructured covariance structure will be used to estimate the within participant variance-covariance. Denominator degrees of freedom will be computed using the Kenward-Roger method. The group mean treatment difference between each dose and placebo at Week 12 will be based on contrasts from this model.

Summary and Analysis of Additional Efficacy Endpoint

The following analyses will generally apply unless otherwise noted in the SAP. For continuous efficacy endpoints, the mean, standard deviation, median, minimum, and maximum will be reported for each treatment group. For endpoints measured at a single post-baseline time point, the between-group treatment summary will be based on an analysis of covariance (ANCOVA) including treatment group, randomization stratum, and baseline for that respective parameter. For endpoints measured at multiple post-baseline time points, the between-group treatment summary at each visit will be conducted using an MMRM including treatment group, visit, treatment-by-visit interaction, and the randomization stratum as fixed effects and the baseline values associated with the endpoint as a covariate. Missing data will not be imputed before performing the MMRM.

Subgroup Analysis for Efficacy

Subgroup analyses of the primary endpoint will be conducted for the following subgroups.

- On symptomatic treatment for AD at baseline: Yes, No
- Sex
- Age: < 65 years or ≥ 65 years and < 75 years or ≥ 75 years

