APPENDIX D. ACTIVITY SCHEDULE

The following table shows the required activities during the study. The individual activities are described in detail in the Operations Manual (Appendix F).

Study Activities Table

Activity	Screening/Visit 1	Screening/Visit 2	Baseline/Day 1 Visit 3	Day 3 /Visit 4 (Telephone Visit)	Week 1 /Visit 5	Week 2 Visit 6	Week 4/Visit 7 (Telephone Visit)	Week 6 /Visit 8	Week 8/Visit 9 (Telephone Visit)	Week 10 /Visit 10 (Telephone Visit)	Week 12/Visit 11 (Premature Discontinuation)	30-Day Follow Up Visit	Unscheduled Visit
Week Relative to Study Drug Start			0	0	1	2	4	6	8	10	12	16	
Day Relative to Study Drug Start			1	3	8	15	29	43	57	71	85	115	
Study Visit Window (days)				±1	±2	±2	±з	±з	±з	±з	±3	±з	
☐ INTERVIEWS & QUESTIO	NNA	AIRES	6										
Informed consent	V												
Eligibility criteria	V												
Medical/surgical history	V												
Alcohol and nicotine use	V												
Adverse event assessment	V	✓	*	✓	✓	✓	✓	✓	✓	*	✓	*	✓
Prior/concomitant therapy	✓	✓	*	✓	✓	✓	✓	✓	✓	*	✓	*	✓
Assess study drug compliance				✓	✓	✓	✓	✓	✓	*	✓		
Assess Altoida DNS performance compliance				1	*	*	*	*	*	*	1		
IMAGING	4												
MRI	V										✓		~
CLINICAL OUTCOMES A	SSE	SSMI	ENTS										
ADAS-Cog 14	V	1	*					✓			✓		✓
C-SSRS	V		✓		✓	✓		✓			✓	*	✓
CDR	V										✓		✓
MMSE	*										>		✓
Cogstate Computerized Battery (CBB and ISLT)	~	*	*		✓	*		✓			1		✓
Altoida DNS (clinic only)	✓	>											>
Altoida DNS (once daily, clinic or home)			✓	✓	✓	✓	✓	✓	✓	✓	✓		
Neuropsychiatric Inventory (NPI)			✓								*		*

Activity	Screening/Visit 1	Screening/Visit 2	Baseline/Day 1 Visit 3	Day 3 /Visit 4 (Telephone Visit)	Week 1 /Visit 5	Week 2 Visit 6	Week 4/Visit 7 (Telephone Visit)	Week 6 /Visit 8	Week 8/Visit 9 (Telephone Visit)	Week 10 /Visit 10 (Telephone Visit)	Week 12/Visit 11 (Premature Discontinuation)	30-Day Follow Up Visit	Unscheduled Visit
Week Relative to Study Drug Start			0	0	1	2	4	6	8	10	12	16	
Day Relative to Study Drug Start			1	3	8	15	29	43	57	71	85	115	
Study Visit Window (days)				±1	±2	±2	±3	±3	±3	±з	±3	±3	
* EXAM													
12-lead ECG	✓										✓		V
Height (screening only) and weight	✓							✓			✓		✓.
Vital signs	✓	✓	*		✓	✓		✓			✓	*	
Physical examination	✓		✓		>	>		\			V	\	
Neurological examination	✓		✓		✓	✓		✓			*	*	
 LAB													
HAV-IgM, HBsAg, HCV Ab, HIV Ab	✓												
Drug and alcohol screen	✓												
Urine pregnancy test (for WOCBP only)			✓			>		>			*		~
Serum pregnancy test (for WOCBP only)	>												

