1.0 Introduction

This Statistical Analysis Plan (SAP) describes the statistical analyses for ABBV-552 Study M23-515, A Randomized, Double-blind, Placebo-controlled, Dose-finding Study to Evaluate the Safety, Efficacy, Pharmacokinetics, and Pharmacodynamics of ABBV-552 in Participants with Mild Alzheimer's Disease (AD).

Study M23-515 examines the efficacy and safety of ABBV-552 in participants with dementia due to mild AD.

The analyses of pharmacokinetic endpoints and plasma biomarkers will not be covered in this SAP.

The SAP will not be updated in case of administrative changes or amendments to the protocol unless the changes impact the analysis.

Unless noted otherwise, all analyses will be performed using SAS Version 9.4 (SAS Institute Inc., Cary, NC 27513) or later.

This SAP includes changes to analyses described in the protocol. Details are outlined in Section 14.1.

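### SAP 9.4.4 adjusts every NPI change score for baseline MMSE instead of the score's own baseline, with no reason given and an expected loss of precision

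*SAP*

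**What the plan says.** SAP 9.4.4 fits one ANCOVA form to the Week 12 change in the NPI: treatment group and "randomization stratum as main effects and the baseline MMSE as a covariate". The same model serves each behavioural domain score, each domain's caregiver distress score, the NPI total and the total distress score. None of these models contains an NPI baseline.

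Protocol 7.4 sets the default for an endpoint with one post-baseline time point, which the NPI is: "analysis of covariance (ANCOVA) including treatment group, randomization stratum, and baseline for that respective parameter". It introduces that default with "The following analyses will generally apply unless otherwise noted in the SAP".

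The other additional endpoints follow the default. SAP 9.4.1 (CDR-SB), 9.4.2 (MMSE), 9.4.3 (Cogstate) and 9.4.5 (ADCOMS) each use the baseline of the measure analysed. The MMSE section reads "randomization stratum as main effects and the baseline MMSE total score as a covariate", almost the same phrase as in the NPI section.

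The activity schedule (Protocol Appendix D) has the NPI at Baseline/Day 1 and Week 12. Before treatment, it has the MMSE only at Screening Visit 1.

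**The concern.** A change score is usually correlated with its own baseline, and adjusting for that baseline removes this part of the variance. It also corrects for chance differences between arms in baseline NPI. A model that adjusts for MMSE instead does neither, except so far as MMSE itself predicts NPI change.

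MMSE is not an obvious substitute. It measures cognition, and eligibility restricts it: "MMSE score of 20 to 26 at Screening Visit 1". It is also taken earlier than the NPI baseline. Protocol 4.1 requires that "Screening Visit 2 must take place at least 7 days after Screening Visit 1 and at least 7 days before Baseline/Day 1", so the MMSE is at least 7 + 7 = 14 days old at Day 1. Meanwhile the Day 1 value on the NPI scale itself goes unused.

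At stake is the width of the interval for each dose-placebo difference on a named efficacy endpoint in a dose-finding study. The primary ADAS-Cog 14 analysis already uses its own baseline and is not touched.

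**Working it through.** **The plan's own figure.** The only design figure is for ADAS-Cog 14: difference 2.85, SD 5.7, 60 per arm less 20% = 48, two-sided 10%, about 80% power. With effect size 2.85/5.7 = 0.5, the normal approximation gives z = 0.5 × √(48/2) − 1.645 = 0.80, or 78.9% power. That reproduces the statement but says nothing about the NPI, for which no SD, correlation or power is given. The 48 per arm is used below for scale only.

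**Formulas.** Let s0 and s1 be the NPI SD at baseline and Week 12, and r their correlation (all assumed).

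- MMSE-adjusted, with MMSE unrelated to NPI change: residual variance = s0² + s1² − 2·r·s0·s1.
- Adjusted for own baseline: residual variance = s1²(1 − r²).
- The first minus the second is (s0 − r·s1)². This is never negative, and it is zero only when the slope of Week 12 on baseline, r·s1/s0, equals 1.
- If MMSE explains a share R² of NPI change, multiply the first line by (1 − R²).

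**Equal SDs.** The variance ratio is 2(1 − r)/(1 − r²) = 2/(1 + r).

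| r | Variance ratio | Interval wider by | 48 per arm worth | Ratio if MMSE explains 10% |
|---|---|---|---|---|
| 0.3 | 1.54 | 24% | 31 | 1.38 |
| 0.5 | 1.33 | 15% | 36 | 1.20 |
| 0.7 | 1.18 | 8% | 41 | 1.06 |
| 0.9 | 1.05 | 3% | 46 | 0.95 |

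Interval width uses the square root of the ratio; the fourth column is 48 divided by the ratio.

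**Unequal SDs, MMSE unrelated to NPI change.**

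| s1/s0 | r = 0.3 | r = 0.5 | r = 0.7 | r = 0.9 |
|---|---|---|---|---|
| 0.8 | 1.99 | 1.75 | 1.59 | 1.65 |
| 1.25 | 1.28 | 1.12 | 1.02 | 1.05 |

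For example, at s1/s0 = 0.8 and r = 0.5: (1 + 0.64 − 0.80)/(0.64 × 0.75) = 0.84/0.48 = 1.75.

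**Simulation.** With 48 per arm, equal SDs, MMSE unrelated to NPI and 8,000 trials per value of r, the variance ratios were 1.51, 1.33, 1.19 and 1.05 at r = 0.3, 0.5, 0.7 and 0.9. The mean error of either estimator was at most 0.0013 SD. This checks the algebra and is not evidence about the trial's NPI data.

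**Chance imbalance in one trial.** With equal SDs, a baseline difference between two arms of 1.96 standard errors is 1.96 × √(2/48) = 0.40 SD. Left uncorrected, it moves the change contrast by (1 − r) times that: 0.20 SD at r = 0.5 and 0.12 SD at r = 0.7. This is the same loss seen from within one trial, not an additional one.

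**The case against.** **The SAP may differ.** Protocol 7.4 allows the SAP to note otherwise, and 9.4.4 names its covariate explicitly. That stands: no breach is alleged. It is also true that the SAP explains none of its covariates in 9.4. But the other sections follow the protocol default and need no explanation; the NPI section is the exception.

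**Intent is unknown.** That the text was carried over from 9.4.2 is an inference, since the sections share a template sentence. It is the most likely cause but is not established. The record of changes does not help: SAP 1.0 states "This SAP includes changes to analyses described in the protocol" and points to 14.1, which lists none.

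**The size rests on assumptions.** This stands in full. The documents support a direction, not a figure, and the range shown includes no loss and even a small gain.

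**The age of the MMSE is a weak point.** The CDR is also collected before treatment only at Screening Visit 1, so the CDR-SB and MMSE analyses use equally old baselines. This is fair. The main point is that the NPI's own baseline is left out.

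**Lack of bias is conditional.** The NPI analysis uses the mITT set without imputation and drops data after a change in AD medication. Randomization alone does not protect that subset under either covariate. What can be said is that the covariate choice adds no bias of its own under randomization with complete data.

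**The consequence is low.** The NPI is one of six additional endpoints, unpowered, in a study without Type I error control. That limits the importance of the point, but the correction uses data already collected.

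**Conclusion.** The concern holds. Every NPI model in SAP 9.4.4 omits the NPI baseline and uses MMSE instead, without a reason and out of line with the other additional endpoints and the protocol default. Precision is expected to be lost. For r between 0.5 and 0.7, with equal SDs and MMSE unrelated to NPI change, intervals would be about 8% to 15% wider, as if 36 to 41 of 48 participants per arm had been used.

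Across the assumptions tried, the variance ratio runs from 0.95 to 1.99. It is 1 when the slope of Week 12 on baseline NPI equals 1 and MMSE explains nothing. The finding is firm on the mismatch and on the expected direction, but not on the size. No power loss is claimed, because no NPI comparison was powered.

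**What to change.** In SAP 9.4.4, replace the MMSE covariate with the baseline value of the NPI score being analysed: the domain score, the domain distress score, the NPI total or the total distress score, as the case may be. If MMSE adjustment was intended, state why and add it beside the NPI baseline instead of in its place.

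The cost is one phrase in a SAP revision and a change of covariate in the program, so that each NPI model picks up its matching baseline. No new data, visits or participants are needed.
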